6.1. Strata and Covariates

Randomisation was planned to be stratified by age at baseline in two strata: 2-<6 months and 6-24 months in a 1:2 ratio. However, as noted in the amended protocol, additional subjects may be enrolled in the older subgroup.

The two age group strata (2-<6 months and 6-24 months) will be the categories used in all tables, figures and listings split by age group unless stated otherwise.

The statistical analysis will be adjusted for age at baseline (as a continuous covariate), sex and a measure of the parameter or severity at baseline as specified in the table below. In addition, the analysis of weight gain will include average calorie intake divided by baseline weight (calorie intake per day per kg).

Patients will be categorised as "Oedematous" if they are recorded on the CRF as having oedema at any time during the study. Otherwise they will be categorised as "Non-oedematous". For each patient, the daily calorie intake (total energy per day) is collected on the CRF. The average of these values divided by baseline weight will be used as the calorie intake covariate.

If an inadequate number of subjects is observed in one of the categories for sex or oedematous status then the covariates may be removed from the models.

In addition to the above, differences between the two treatment groups (emollient therapy versus no emollient) will be examined with respect to baseline characteristics prior to performing statistical analysis of the efficacy endpoints. If any differences are considered to be clinically important, exploratory subgroup analysis may be presented for the relevant endpoints.

Depending on the method of statistical analysis, covariates/factors specified below will be fitted in each model. If any terms are not significant then they may be dropped from the final analysis.

Method of analysis	Endpoints]	Fixed effects te	erms	Random effects terms
		Continuous Covariates	Factors	Interactions	Covariates
ANCOVA	Fatty Acids	Baseline of parameter, age	Treatment, sex		
MMRM	Weight	Baseline of parameter,	Treatment, day, sex,	Baseline of parameter	Subject (in the subject
	TEWL	age, calorie intake per	oedematous status	*day, treatment*day,	option of the repeated
	Skin redness	day per kg ^[2] , mean breast		treatment*age category, treatment*age	statement in proc mixed)
	Skin Appearance	feeding frequency ^[2]		category*day ^[3]	
Cox	Discharge	Baseline	Treatment,		
proportional	from acute	weight-for-	sex		
hazard	phase	length Z			

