model		score, age			

Table 1: Covariates/Factors to be included in statistical analyses

Logistic	Suspected	Baseline	Treatment,	
regression	nosocomial	weight-for-	sex	
	infections	length Z		
		score, age		

- [1] Oedematous status and calorie intake was only to be included in the analysis of weight at interim. After interim, since there were only 4 subjects with oedema, the decision was taken to remove subjects with oedema from the statistical analysis. Oedematous status was therefore removed as a covariate.
- [2] Based on further information from the data and from site the decision was taken to adjust for calorie intake per day per kg rather than calorie intake. Also, it was decided to use mean breast feeding frequency as a covariate for the weight analysis only
- [3] The additional interactions of treatment*age category and treatment*age category*day was included after the review of interim analysis results to investigate the differences in endpoints between the two age categories. Note, the age categories are: 2-<6 months and 6-24 months.
- [4] Note, the statistical analysis of endpoints related to the skin and gut microbiome data is not included here, because this analysis will be performed by experts in the field at Stanford University, California, USA. Also, the analysis of the metabolomic data will be performed by a CRO Metabolon with additional input from representatives of the GSK subsidiary company Cellzome.

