- Rate of weight gain (g/kg/day)
- Rate of weight gain (g/kg/day) by oedematous status

Relative change from baseline will also be plotted over time. Day will be presented on the x-axis and the relative change from baseline will be presented on the y-axis. The mean at each day will be presented with an associated 95% confidence interval (CI). The plot will be repeated for the rate of weight gain.

Additionally, the WAZ, WLZ and LAZ scores will be presented over time using simple descriptive statistics tables and graphical plots. Further exploratory statistical analyses may be performed for one or more Z scores if the review of data warrants so.

Mixed model repeated measures analysis

Rate of weight gain (g/kg/day) will be analysed using a mixed model repeated measures (MMRM) analysis with restricted maximum likelihood estimation and an unstructured variance-covariance matrix. Covariates/ factors will be included in the model as

described in Section 7.1**Error! Reference source not found.** In the circumstance that there are convergence problems with the MMRM analysis, this will be explored. For example the SCORING=4 option could be used in the MIXED statement, which makes SAS use Fisher scoring for the first 4 iterations. If the convergence problem cannot be resolved then alternative covariance structures will be investigated.

The estimate of treatment differences for "Emollient Therapy – No Emollient" at each day will be displayed in the summary of statistical analysis together with the 95% CI and the associated p-value. Least Squares Means for each day will also be presented with the standard error and the number of subjects contributing to the Least Squares Means.

The least squares mean at each day will be plotted by treatment group. Day will be presented on the x-axis and the rate of weight gain will be presented on the y-axis. The mean at each day will be presented with an associated 95% CI.

If any of the covariates are statistically significant then post-hoc analyses may be conducted to investigate further.

The normality assumptions will be assessed by inspection of the following plots:

Histogram of marginal studentised residuals derived from the MMRM model

• Normal probability plot

Bayesian analysis

At the interim analysis stage, Bayesian methods of analysis will be used to estimate the posterior distribution for the treatment difference in rate of weight gain between emollient therapy and no emollient at day 10 for the ITT population.

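### Section 6.1 lets non-significant terms be dropped from the Table 1 models, including age, the randomisation stratification variable, with no threshold and no protected term

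*SAP*

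**What the plan says.** Section 6.1 of the SAP states the stratification: "Randomisation was planned to be stratified by age at baseline in two strata: 2-<6 months and 6-24 months in a 1:2 ratio". It then commits to adjustment: "The statistical analysis will be adjusted for age at baseline (as a continuous covariate), sex" and a baseline measure of the parameter or of severity. The lead-in to Table 1 reads "Depending on the method of statistical analysis, covariates/factors specified below will be fitted in each model", and the next sentence adds: "If any terms are not significant then they may be dropped from the final analysis".

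Table 1 covers four kinds of model:

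- ANCOVA for fatty acids. Section 1.2 puts this analysis outside the plan and Section 9.8 gives it to an external group.
- MMRM for weight, TEWL, skin redness and skin appearance.
- Cox regression for discharge from the acute phase.
- Logistic regression for suspected nosocomial infection.

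Age is a continuous covariate in all four. Age category enters only the MMRM, through interactions; footnote [3] says: "The additional interactions of treatment*age category and treatment*age category*day was included after the review of interim analysis results". Sections 9.1, 9.2 and 9.3 refer back to these covariates, under the number 7.1.

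**The concern.** The section promises adjustment and then lets the final data withdraw it. A non-significant p-value does not show that a prognostic or stratification variable is unneeded; with modest numbers it often shows only low power for that term. Because removal is permitted rather than required, and no threshold is set, several models are admissible for the same endpoint.

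Section 1.2 describes the trial as open-label, and the plan reports 95% confidence intervals for the modelled treatment effects, with p-values for the MMRM and Cox analyses. Those intervals take the fitted model as fixed in advance and do not reflect the selection step. In the Cox and logistic models, the treatment ratio conditional on a prognostic covariate is not the same quantity as the ratio without it, so dropping weight-for-length Z or age can change what is estimated as well as its precision.

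**Working it through.** The plan gives no figure on this point to reproduce: it states no sample size, effect size or standard deviation, and refers sample size to the protocol. The check is a reading of the text plus illustrations on stated assumptions.

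**1. Which terms are exposed.** No term in Table 1 is exempted. In the Cox and logistic models, continuous age is the only carrier of the stratification variable, so losing it leaves no age term. In the MMRM the rule, read literally, covers treatment-by-day and the age-category interactions. Section 9.1 requires a treatment difference at each day, and estimates by age category and overall from a single model. Those outputs cannot be produced without the interactions, so the rule and Section 9.1 conflict.

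**2. Covariate dropping in a linear model.** Assumed, not in the SAP: N = 100 or 200, 1:1 arms within strata, strata 1:2, baseline–outcome correlation 0.3, sex unrelated to outcome, no treatment effect, dropping threshold 0.05, 6,000 runs per row. Fit outcome on treatment, age, sex and baseline; drop each covariate with p ≥ 0.05; refit. The last column is the mean absolute change in the treatment estimate, in units of its standard error (SE).

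| N | Age–outcome correlation | Age dropped | Type I, full | Type I, reduced | Type I, smaller p | Shift (SE) |
|---|---|---|---|---|---|---|
| 100 | 0 | 95% | 4.88% | 5.03% | 5.33% | 0.08 |
| 100 | 0.1 | 82% | 5.60% | 5.85% | 6.17% | 0.09 |
| 100 | 0.2 | 44% | 5.13% | 5.43% | 5.72% | 0.08 |
| 100 | 0.3 | 10% | 4.58% | 4.98% | 5.13% | 0.07 |
| 200 | 0 | 95% | 4.98% | 5.07% | 5.33% | 0.05 |
| 200 | 0.1 | 69% | 4.87% | 4.90% | 5.28% | 0.05 |
| 200 | 0.2 | 16% | 4.43% | 4.60% | 4.82% | 0.05 |
| 200 | 0.3 | 0.5% | 4.78% | 4.58% | 4.83% | 0.04 |

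Taking the smaller of the two p-values adds between 4.83 − 4.78 = 0.05 and 5.72 − 5.13 = 0.59 points. Plain dropping changes the rate by between −0.20 (4.58 − 4.78) and +0.40 (4.98 − 4.58). The Monte Carlo standard error of one rate is √(0.05 × 0.95 / 6000) = 0.28 points. A second check (N = 200, three covariates with effects 0, 0.1 and 0.2 SD, 4,000 runs) gave 4.6–5.1% for the full model and 5.1–5.4% after dropping once, an addition of about 0.1 to 0.5 points. Age is therefore often lost when weakly prognostic, with little effect on the error rate.

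**3. If treatment-by-day were dropped.** Assumed: no treatment effect, five post-baseline visits (as for TEWL in Section 9.4), known compound-symmetric covariance with correlation ρ of 0.3 to 0.7, threshold 0.05, no other treatment-by-time term. The interaction is non-significant in 95% of trials. Scale the Day 10 difference to variance 1. Without the interaction, the Day 10 estimate becomes the all-visit mean. The two differ with variance 0.8(1 − ρ), so the mean absolute gap is √(2/π) × √(0.8(1 − ρ)):

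- ρ = 0.3: 0.798 × 0.748 = 0.60 SE.
- ρ = 0.7: 0.798 × 0.490 = 0.39 SE.

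Among the 95% of trials where the term could be dropped, these become 0.57 and 0.37. Choosing the smaller p-value rejects in 7.2–8.3% of trials, against 5.0%.

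**4. Cox and logistic.** These were not simulated. The change in estimand follows from the models; its size depends on how prognostic the dropped covariate is, which the SAP does not say.

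**The case against.** The strongest reply is that the study is exploratory. Section 6 says so of all analyses, and Section 6.2 makes no multiplicity adjustment and asks for p-values to be read in the context of the wider results. The plan does not claim control of type I error, and the effect on it is small anyway. That stands as a limit on seriousness. It does not justify an undefined model, since a reported interval should still match the analysis that produced it.

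Four stronger readings are tempting and are not supported:

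- *Every efficacy endpoint is affected.* SCORDoK, CRP and cytokines (Sections 9.7, 9.9, 9.10) are only summarised, so there is no adjusted estimate to change.
- *Type I error is materially inflated.* A search for the smallest p-value over all permitted subsets of six weak covariates (N = 200 assumed, 1,500 runs per setting) gives 6.2–7.7%, against 5.1–5.6% for the full model. That is deliberate selection on the treatment p-value, with more covariates than Table 1 implies: three main-effect adjusters in most models and five for weight. The sentence concerns the significance of the terms, and nothing in the SAP says analysts would choose on the treatment effect.
- *The interactions will in practice be lost.* Section 9.1's promised outputs presuppose them. What stands is that the two texts conflict.
- *Other sentences show the same defect.* The sparse-category rule, "If an inadequate number of subjects is observed in one of the categories for sex or oedematous status then the covariates may be removed", turns on category size and names only sex and oedema. The Section 9.1 sentence, "If any of the covariates are statistically significant then post-hoc analyses may be conducted to investigate further", adds post-hoc work and removes nothing.

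**Conclusion.** The point holds for the endpoints modelled in Table 1, with fatty acids included only where the ANCOVA is run. The dropping sentence contradicts the adjustment commitment in its own section, leaves the stratification variable unprotected, and conflicts on its face with the by-day and by-age outputs of Section 9.1.

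The error-rate cost of dropping covariates in linear models is small, about 0.1 to 0.6 percentage points, and the treatment estimate moves by 0.04 to 0.09 SE on average. Both figures rest on the assumed sample sizes, correlations and 0.05 threshold. The larger figures for treatment-by-day apply only if the literal reading were acted on. The substance of the point is a data-dependent model with intervals that ignore the selection and, in the Cox and logistic models, an unquantified change in the conditional ratio. This should be corrected; it does not invalidate the trial.

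**What to change.** Delete the dropping sentence from Section 6.1. State instead that treatment, age as specified in Table 1, sex and the baseline measure stay in every model whatever their p-values, and that in the MMRM day, baseline-by-day, treatment-by-day and the age-category interactions stay as well. Any reduced model should appear only as a labelled sensitivity analysis beside the full one.

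Keep age in its Table 1 form; recoding it as a Cox stratum or as a factor is a separate modelling choice that this point does not require. Calorie intake and breast-feeding frequency in the weight model are averages over study days rather than baseline values. Whether they belong is also a separate question, but it should not be settled by their p-values.

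The cost is a short edit and a few degrees of freedom for the covariates. The interactions are needed for the Section 9.1 outputs in any case.

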6.2. Multiple Comparisons and Multiplicity

As this is an exploratory study, no adjustment will be made for multiple testing. When interpreting individual p-values for the endpoints, care will be taken to consider the results as part of the wider study results.

6.3. Missing Data

No imputation will be carried out for missing data or subjects who withdraw early. Data from children withdrawn because of failure to respond to the usual management of SAM, or voluntary dropouts will be included in the analysis up to the time of withdrawal. A supplementary analysis excluding the children withdrawn may be performed.

An exception to this is the Mean Breast Feeding Frequency variable for the Weight Gain analysis. In cases where there were missing values for all ten days, the mean value was imputed to be 0 rather than missing for modelling purposes.

7. DERIVED DATA

7.1. Baseline

For assessments that were collected on the daily monitoring chart, baseline is considered to be the subjects Day 1 assessment as collected on the CRF. For all other assessments, baseline is considered to be the subject's Day 0 assessment as collected on the CRF. If there are multiple assessments on Day 0 (or Day 1 for assessments from the daily monitoring chart) then the earliest will be taken as the baseline.

Change from baseline for post-baseline records will be calculated by subtracting the baseline value from the post-baseline value. If either the baseline or post-randomisation value is missing, the change from baseline is set to missing.

Percentage Change from Baseline will be calculated as

7.2. Study Day

As noted in section 8.1, study days have been recorded or labelled differently across different CRF forms. Study days are recorded from day 1 to day 11 on the daily monitoring chart, day 1 to day 10 on the Emollient record and Calorie intake CRF and from day 0 to day 10 in the other CRFs. Therefore, it is possible that the same date will be assigned a different study days across different domains. Following review of interim analysis results, in order to resolve this inconsistency or confusion in reporting, all study visits will be presented from Day 0 to Day 10. See Table 2 below for further clarification.

Table 2: Clarification of Study day to be used during final reporting	

Label to be used throughout the final study report	Day as recorded in the Daily Monitoring Chart (CRF/Dataset)	Day as recorded in the Emollient record and Calorie intake (CREs/Datasets
Day 0	Day 1	Day 1
Day 1	Day 2	Day 2
Day 2	Day 3	Day 3
Day 3	Day 4	Day 4
Day 4	Day 5	Day 5
Day 5	Day 6	Day 6

Day 6	Day 7	Day 7
Day 7	Day 8	Day 8
Day 8	Day 9	Day 9
Day 9	Day 10	Day 10
Day 10	Day 11	

Note: Label Day 0 is also referred to as baseline in this RAP.

Assessments that were collected three times a day on the daily monitoring chart will have the time of assessment included in the day description. For example, day 1 will have the following labels: Day 1 9AM, Day 1 5PM and Day 1 1AM. For variables with multiple assessments on a given study day, first available assessment value will be used for the analysis.

8. STUDY POPULATION

8.1. Disposition

The number and percentage of subjects who completed the study and withdrew prematurely from the study will be presented by treatment group for the Safety population. The table will also summarise the reason for premature withdrawal.

8.2. Demography

Demographic characteristics will be summarised by treatment group for the Safety Population. Summary statistics (number of subjects, mean, and standard deviation, median, minimum and maximum) will be presented for age (months), weight (kg) and height (cm) at Day 0. The number and percentage of subjects will be presented for sex and age group (2-<6 months, 6-24 months) at Day 0.

8.3. Baseline Characteristics

Summary statistics for the weight-for-length Z (WLZ) score, length-for-age Z (LAZ) score, weight-for-age Z (WAZ) score, mid upper arm circumference, mother's / caregiver's formal years of education, father's formal years of education and duration of exclusive breast feeding at Day 0 will be summarised by treatment group for the Safety population. The number and percentage of subjects will also be presented for, presence of oedema, breast feeding history (no breast feeding since birth, partial breast feeding or exclusive breast feeding), breast feeding status (still breast feeding, not still breast feeding), type of diarrhoea and presence of pneumonia, sepsis/septicaemia, meningitis/encephalitis, vitamin A deficiency, skin infection, ileus, ASOM/CSOM, enteric fever and other clinical diagnosis and visible wasting at Day 0.

For the interim analysis only, differences between the two treatment groups (emollient therapy versus no emollient) for each baseline characteristic will be examined. For continuous data a two sample t-test will be carried out to compare the two treatment groups. If the data is not normally distributed then a non-parametric Wilcoxon rank sum test may be used instead. For categorical data a chi-squared test will be used.

9. EXPLORATORY EFFICACY ANALYSES

All efficacy tables, listings and figures will use the ITT population unless specified otherwise.

9.1. Weight

Derivations

Weight is collected once every day (approximately at 9 am) and recorded on 'daily monitoring chart' for all participants. However, for intervention group only, weight is measured three times daily (approximately at 9 am, 5 pm and 11 pm) and recorded on 'Emollient application record' to measure the intervention material. The summaries and analysis of weight gain will be based on the daily 9AM measurements on 'Daily monitoring chart' only, however, all measurements will be considered in the derivation of baseline weight. Data from baseline up to and including day 10 (labelled as Day 1 to Day 11 on the daily monitoring chart CRF) will be included in the weight analysis as per the specification on the eCRF. At the time of interim and post interim, a footnote will be included to indicate this.

Weight measurements that were collected while a subject had detectable oedema will be excluded from the summaries and analysis. The earliest measurement in the daily monitoring chart where oedema status was recorded as 1 (no oedema) will be taken as the baseline weight. Following review of the interim analysis results, it was decided that all subjects with oedema would be excluded from the weight analysis only. Subjects with oedema would be summarised separately in the final clinical study report.

Weight will be summarised as a rate of weight gain (g/kg/day), as defined below:

Change from Baseline in Weight at Day X (g)	=	Weight at Day X (g) – Weight at Baseline (g)
Relative Change from Baseline	=	Change from Baseline in Weight at Day X (g)

in Weight at Day X (g/kg)

Weight at Baseline (kg)

Rate of Weight Gain at Day X (g/kg/day) Relative Change in Weight at Day X (g/kg)

Note: 'X' refers to the study day label (see Table 2, page 10) and not the day reported on the daily monitoring chart

Summary Statistics

The following endpoints will be summarised by day (day 0 - day 10), presenting the number of subjects, mean (with standard deviation) and median, minimum and maximum for each treatment group. The summaries for change from baseline, relative change from baseline and rate of weight gain will also present summary statistics for the last day the subject was in the study.

- Weight (kg)
- Weight (kg) by oedematous status
- Change from baseline in weight (g)
- Change from baseline in weight (g) by oedematous status
- Relative change from baseline in weight (g/kg)
- Relative change from baseline in weight (g/kg) by oedematous status
- Rate of weight gain (g/kg/day)
- Rate of weight gain (g/kg/day) by oedematous status

Relative change from baseline will also be plotted over time. Day will be presented on the x-axis and the relative change from baseline will be presented on the y-axis. The mean at each day will be presented with an associated 95% confidence interval (CI). The plot will be repeated for the rate of weight gain.

Additionally, the WAZ, WLZ and LAZ scores will be presented over time using simple descriptive statistics tables and graphical plots. Further exploratory statistical analyses may be performed for one or more Z scores if the review of data warrants so.

Mixed model repeated measures analysis

Rate of weight gain (g/kg/day) will be analysed using a mixed model repeated measures (MMRM) analysis with restricted maximum likelihood estimation and an unstructured variance-covariance matrix. Covariates/ factors will be included in the model as

described in Section 7.1**Error! Reference source not found.** In the circumstance that there are convergence problems with the MMRM analysis, this will be explored. For example the SCORING=4 option could be used in the MIXED statement, which makes SAS use Fisher scoring for the first 4 iterations. If the convergence problem cannot be resolved then alternative covariance structures will be investigated.

The estimate of treatment differences for "Emollient Therapy – No Emollient" at each day will be displayed in the summary of statistical analysis together with the 95% CI and the associated p-value. Least Squares Means for each day will also be presented with the standard error and the number of subjects contributing to the Least Squares Means.

The least squares mean at each day will be plotted by treatment group. Day will be presented on the x-axis and the rate of weight gain will be presented on the y-axis. The mean at each day will be presented with an associated 95% CI.

If any of the covariates are statistically significant then post-hoc analyses may be conducted to investigate further.

The normality assumptions will be assessed by inspection of the following plots:

Histogram of marginal studentised residuals derived from the MMRM model

• Normal probability plot

Bayesian analysis

At the interim analysis stage, Bayesian methods of analysis will be used to estimate the posterior distribution for the treatment difference in rate of weight gain between emollient therapy and no emollient at day 10 for the ITT population.

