1.2. Endpoint(s)

This is an exploratory open-label study to evaluate potential benefits of topical application of (SSO in SAM. There is little or no historical data available on efficacy endpoints, therefore an interim analysis was planned when 100 evaluable subjects have completed the study. The results from the interim analysis will help identify key/primary efficacy endpoints. Therefore, the list of endpoints and analysis plan may be updated after the interim analysis.

The endpoints which will be investigated in the analysis are:

Primary Endpoints

• Weight gain (g/kg/day)

Secondary Endpoints

- Time (days) to discharge from acute phase
- Rate of suspected nosocomial infections (nosocomial infection will be diagnosed clinically as per hospital's management guidelines where it has been mentioned that any new sign of infection during hospital stay that was not present at admission will be considered as nosocomial infection. Following the interim analysis, the list of nosocomial infections was restricted to pneumonia, fever, UTI and sepsis.)
- Change from baseline in transepidermal water loss (TEWL) at Day 10
- Change from baseline in plasma fatty acid levels at Day 10*
- Change from baseline in c-reactive protein (CRP) at Day 10
- Change from baseline in pro-inflammatory cytokine parameters at Day 10

- Clinical improvement of visual skin condition:
 - Change from baseline in skin redness at Day 10
 - \circ Change from baseline in skin condition score at Day 10
- Change from baseline in the skin and gut microbiome data at Day 10*
- * Change from baseline in plasma fatty acid levels at day 10 will not be included in the interim analysis as the results will not be available until the end of the study. The analysis of plasma fatty acid levels will be included in the final study report. However, this analysis is outside the scope of this RAP.
- * Change in the skin and gut microbiome data will be collected for a sub-sample of subjects in the study as described in the protocol amendment. This analysis will be performed at the end of the study by an external expert at Stanford University. The metabolomic data will be analysed by the CRO (Metabolon) and additional support will be provided by the GSK subsidiary company Cellzome. As previously indicated, the analysis of skin and gut microbiome data is outside the scope of this RAP.

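### Section 9.1 gives two conflicting sources for baseline weight, one of which includes a record kept only in the emollient arm

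*SAP*

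**What the plan says.** Section 9.1 (Weight, Derivations) describes two weight records. The first covers everyone: "Weight is collected once every day (approximately at 9 am) and recorded on 'daily monitoring chart' for all participants". The second is the emollient application record, kept to measure the intervention material: "for intervention group only, weight is measured three times daily (approximately at 9 am, 5 pm and 11 pm").

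For the analysis, section 9.1 starts with a restriction: "The summaries and analysis of weight gain will be based on the daily 9AM measurements on 'Daily monitoring chart' only". The same sentence then makes an exception for baseline: "however, all measurements will be considered in the derivation of baseline weight".

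The next paragraph gives a different baseline rule: "The earliest measurement in the daily monitoring chart where oedema status was recorded as 1 (no oedema) will be taken as the baseline weight". Section 7.1 (Baseline) agrees with this second rule as to source: "For assessments that were collected on the daily monitoring chart, baseline is considered to be the subjects Day 1 assessment as collected on the CRF". Where the baseline day has several assessments, section 7.1 says "then the earliest will be taken as the baseline".

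The SAP does not say which of the two rules in section 9.1 governs.

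**The concern.** Baseline weight enters the primary endpoint twice: it is subtracted from the Day X weight, and it is the kilogram denominator. It is also the baseline covariate in the repeated-measures model and the divisor of the calorie-intake covariate (sections 6.1 and 9.1).

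The chart holds one weight per day. In a sentence that has just confined the analysis to that chart, the exception for all measurements most naturally brings in the other record described, which control children do not have. Table 2 in section 7.2 maps Day 1 of that record to Day 0, so emollient-arm weights can exist on the baseline day.

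Two programmers could therefore derive different primary endpoints from the same data. One of the two derivations would use different source records by arm. Randomisation does not protect against a difference in how baseline is obtained. Adjusting for baseline does not remove it either, because the covariate itself would be obtained differently by arm.

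**Working it through.** The SAP gives no figure on this point, so there is none to reproduce. The check has two parts.

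**1. The two rules side by side**

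| | All-measurements clause (9.1) | Chart rule (9.1, next paragraph; source as in 7.1) |
|---|---|---|
| Records, emollient arm | Chart plus emollient record | Chart |
| Records, control arm | Chart | Chart |
| Selection | None stated; earliest, if 7.1 is applied | Earliest weight without oedema |
| Same source in both arms | No | Yes |

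Suppose the earliest usable value is taken from the pooled records. An emollient child's baseline then differs from the chart rule only if no usable chart weight comes first. Even then the emollient record has its own weighing at about 9 am. A 5 pm or 11 pm weight becomes baseline only if no 9 am weight from either record is usable that day. A control child in that position waits for the next 9 am chart weight.

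**2. Sensitivity of the endpoint**

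Section 9.1 defines relative change as change in grams over baseline weight in kg. Dividing by X days follows from the unit g/kg/day. With W0 the baseline weight and WX the weight at Day X, in kg:

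R(X) = (1000 / X) × (WX / W0 − 1)

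If the baseline used is (1 + d) × W0, the rate changes by

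Δ(X) = (1000 / X) × (WX / W0) × (1 / (1 + d) − 1), or about −1000d / X.

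The arm mean changes by f × Δ(X), where f is the share of emollient children affected.

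The inputs are assumptions, since the SAP gives none of them: a shift d of 1% either way (50 g in a 5 kg child), a true gain of 5 g/kg/day, and f of 5% or 10%.

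- Day 10, d = −1%: 100 × 1.05 × (1/0.99 − 1) = +1.06 g/kg/day per affected child.
- Day 10, d = +1%: 100 × 1.05 × (1/1.01 − 1) = −1.04.
- Day 1, d = −1%: 1000 × 1.005 × (1/0.99 − 1) = +10.15.
- Day 1, d = +1%: 1000 × 1.005 × (1/1.01 − 1) = −9.95.

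Change in the emollient-arm mean (g/kg/day):

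| Share affected | Day 10, baseline 1% lower | Day 10, 1% higher | Day 1, 1% lower | Day 1, 1% higher |
|---|---|---|---|---|
| 5% | +0.05 | −0.05 | +0.51 | −0.50 |
| 10% | +0.11 | −0.10 | +1.02 | −1.00 |

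The first-order form gives 0.05 and 0.10 at Day 10, and 0.5 and 1.0 at Day 1.

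For a single affected child, a shift of 20 to 100 g moves the Day 10 rate by about 0.7 to 3.6 g/kg/day at an assumed 3 kg, 0.4 to 2.1 at 5 kg and 0.3 to 1.5 at 7 kg. A 1% lower baseline also raises that child's calorie intake per kg by about 1% (1/0.99 = 1.010).

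If baseline comes from the chart in both arms, f = 0 and this mechanism contributes nothing.

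**The case against.** The strongest reply is that the SAP already has a usable rule. The all-measurements clause says only that weights will be considered and names no algorithm. The next paragraph does name one, and it is common to both arms. If that rule governs, the arms are treated alike. The clause might also mean only that chart weights from any day may be searched for the first one without oedema, which is harmless. Both readings are possible. But the clause is set against a restriction to the chart, directly after the arm-specific record is described, and nothing in the text limits it to the harmless meaning. The contradiction stands.

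The reply is right about size. With an earliest-value rule, few children are likely to be affected, and the emollient record's own 9 am weight narrows the mechanism further. Averaging all baseline-day weights would affect the whole emollient arm, but it has no support in the text, because section 7.1 takes the earliest value.

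A reader might infer that the primary endpoint is biased in favour of the emollient by something near 1 g/kg/day. The SAP does not support that. A shift of that size at Day 10 needs roughly a 1% error in every emollient child. The direction is also open: a weight taken later in the day could be higher or lower, and the SAP does not say which. Nor is 1 g/kg/day a decision limit for the final analysis. It appears only among the posterior-probability cut-offs of the interim Bayesian table in section 9.1, which also says that no Bayesian analysis is planned at the end of the study.

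**Conclusion.** Section 9.1 contradicts itself on the source of baseline weight, and one of its two rules lets that source differ by arm. This should be corrected because it concerns the starting value and denominator of the primary endpoint, in an open-label study whose analysis plan was revised after interim results.

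The finding is a conflict to resolve, not a demonstrated bias. The likely effect at Day 10 is small, about 0.05 to 0.10 g/kg/day in either direction if 5 to 10% of emollient children had a baseline 1% off. It is about ten times larger at Day 1, which matters because the model reports a treatment difference and p-value at each day. The shares and the shift are assumptions; the SAP gives no count of children without a usable first chart weight.

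**What to change.** Delete from section 9.1 the clause "however, all measurements will be considered in the derivation of baseline weight", or limit it expressly to the daily monitoring chart. Keep one rule: in both arms, baseline weight is the earliest 9 AM daily-monitoring-chart weight recorded without oedema. State that weights on the emollient application record are not used for baseline weight or for the calorie-per-kg covariate.

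Leave two things as they are. The oedema-free condition is still needed, because section 9.1 continues to summarise weight by oedematous status. The definition of X as the study-day label should also stay, since changing the divisor would change the endpoint and is not needed to remove this conflict.

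The cost is a wording change in the SAP. It needs no new data and changes no sample size. Some emollient children may get a slightly later baseline, and any baseline already derived from the emollient record would have to be derived again.
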